Research staff can place the reminder call whenever they think makes the most sense. Some people prefer to place a reminder call the day before and then also call the participant in the morning to confirm that they are still planning on the appointment. Other staff may prefer to call the participant the morning of the appointment. Regardless of timing, there needs to be at least one reminder phone call placed and logged in DatStat. Research staff can feel free to log all of their contact calls but at a minimum they need to log one contact.

Phone call talking to a real person

“Hi, my name {U:RA_FIRST} {U:RA_LAST} from {U:DATSTAT_SITE}. I was calling to remind you that I have an appointment set up with you to do your final 12 month survey for the Aging in Place Study. Your appointment is scheduled for {U:12MONTH_DATE} at {U:12MONTH_LOCATION}. Does this time still work for you?”

If yes, “Great, I look forward to seeing you soon. Please call me if you have any questions. My phone number is {U:RA_TELEPHONE} and my name is {U:RA_FIRST} {U:RA_LAST}

If no, ask them if we can find another time to set up the appointment. Research staff works to set up a time for the interview. Change in appointment date is documented in DatStat.

Phone call voicemail

“Hi, my name is name {U:RA_FIRST} {U:RA_LAST} from {U:DATSTAT_SITE}. I was calling to remind you that I have an appointment set up with you to do your 12 month follow-up survey for the Aging in Place Study. Your appointment is scheduled for {U:12MONTH_DATE} at {U:12MONTH_LOCATION}. If this time still works for you I do not need a call back. If you have

decided you would no longer like to participate in the study or would like to change your appointment time please feel free to give me a call back. My phone number is {U:RA_TELEPHONE}. Thanks and have a nice day. “

Please refer to 12 month survey for instructions on 12 month data collection.

Medical Chart Review

The purpose of the Medical Chart Review Component of the Study is to see if the number of times participants report visiting the Emergency Department or staying overnight in the Hospital is consistent with what is found in the medical record.

Before the next in person visit

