Prior to the next in person visit research staff should confirm that the participant signed the consent form for the medical chart review component of the study. If the participant has signed the consent form researcher staff should complete an authorization for release of medical records for the participant. Research staff need to complete the Patient Information section of the form and the date range on the Medical Records to be disclosed section. Research staff should bring two copies of the authorization for release of medical information form to the visit. Research staff should also have a copy of the medical records review form for reference.

At the in person visit

During the in person visit, at some point the research staff should remind participants about the second component of the study that involves requesting their medical records to confirm that they visited the emergency room and stayed overnight in the hospital on the days that they said they did. Research staff will review the authorization of release of medical information form with the participant and will confirm that the only medical information we are requesting is related to the dates you visited the Emergency Department and the nights the participant spent in the hospital. Research staff will ask participants to sign the authorization of release of medical information form and will leave an extra copy with the participant.

After a participant has signed the Authorization of Release of Medical Information Form

Once a participant has signed the release form and once they have completed the study (completed the endline survey or met a main outcome), research staff will copy the authorization file and will keep the original in a locked filing cabinet. They will fax a copy of the authorization form and a cover page (see supporting documents) to the medical records department at every hospital where the participant reported visiting in the last year. We will track the progress of the submission of the requests via our data collection program, DatStat.

Follow up with Medical Offices

We will follow up with the medical records department every four weeks to ensure they are processing our request.

Receipt of Medical Records

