All medical records will be faxed to [name] in Madison, WI. Once we receive a patient's medical record we will enter the dates of hospitalizations and emergency department visits into DatStat using the Medical Record Review Form 1 and Medical Record Review Form 2. All medical records will be kept in a locked drawer in a locked office suite.

Accessing medical records for people who have died

If a participant dies prior to us accessing their medical records, we will request the legal guardian or spouse to sign a new form giving us permission to access their medical records.

Accessing medical records for people who withdraw from the study

If prior to the end of the study a participant withdraws from the study, we will ask them if it is still okay for us to access their medical records. We will remind them that they previously gave us permission to do so and that this will require no additional work on their part. If a participant agrees to this then we will follow the protocol above for accessing medical records.

Unexpected Circumstances

Some trouble shooting situations:

- If the client wants to give you food or drinks politely refuse and stress the quicker we can get the questionnaire done he/she can get back to their regular schedule.
- Participant gets tired in the middle of the questionnaire or you can tell they have lost their attention span to answer the questions. Try to complete study but if not you could try to finish questions over the phone making it easier so you don't have to go back to their homes. Payment will be sent to participant upon completion of the survey if applicable
- If there are interruptions (family comes home, friend comes by to visit, package gets dropped off, etc.) while questionnaire is being asked allow time for the participant to focus back to the task at hand.
- Canceling last minute may be an issue just be sure to make follow up phone calls to reschedule.
- Not home/forgot here the phone call the day before the scheduled time is important so they don't forget you are supposed to come over.
- For the control group a problem we may face is the fact that they don't know who the organization is and we could have higher refusals for that group.

Exiting the Study

At any time a participant has the right to exit the study. In this case you will answer the following questions on behalf of the participant and then they will not be contacted again for the purposes of the study.

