Why is the participant leaving the study? (DATSTAT_EXITREASON)

Completed

Deceased

Censored (moved to a higher level of care- i.e. independent care to assisted living)

Unable to Continue (you should mark this answer if the person is too sick to continue)

Unable to Locate

Unwilling to Continue
Withdrawn by study staff
Unknown

What day did this person exit the study? (DATSTAT_EXITDATE)

What other information should we know about why this person left the study?
(DATSTAT_EXITCOMMENT)

Missing Data Points for a Participant

If study staff are not able to contact a participant within the appropriate window of data collection they have not exited the study but this is considered missing data. We will continue trying to contact the participant at every data collection point unless they contact us directly and ask to withdraw from the study. If research staff “miss” a data collection point, they should still try to collect the data but will have to follow the following protocol to ensure data is collected accurately:

Our DatStat workflow set up in your configuration is such that the time point gets updated when EITHER of the following occurs: 1) the survey for that timepoint gets submitted, OR 2) the time point goes out of window. For this participant, the 3 month call went out of window, and thus the timepoint got updated to 6 months.

In order to enter data for the 3 month survey at this point, the following must occur:

1. The participant must be edited and their time point set back to “3 months”
2. The current open survey (study task = “3 month survey”) must be closed by clicking Edit Survey next to the task in the Study Task grid, and changing the status to Final Incomplete
3. A new 3 month survey study task must be added. To do this, while in the study Task grid go to the Take Action menu and select Add Survey. Select the survey called “3 month Survey (Ad hoc)”. Schedule the survey, and select the Survey Pending status code, and click save. You may now use this task to enter your 3 month data. DO NOT do this until you’ve done steps 1 and 2.

Any time you make a change like this you need to mark down in your study log that you are making this change and mark down in your survey that this was collected out of window and the reason why. You also need to alert [name] that this change is made and she will record it in the data log,

Reentry into the study after exited**

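### The hospital-records request has no trigger for signers who become too sick, cannot be located or never give an endline, so the check of self-report is selective

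*Protocol*

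**What the plan says.** The Protocol's Medical Chart Review section sets out to learn whether the number of emergency department visits and overnight stays that participants report "is consistent with what is found in the medical record". The release is presented at an in-person visit after the chart-review consent has been confirmed. The first such visit after baseline is the 6-month survey.

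The request itself waits: "Once a participant has signed the release form and once they have completed the study (completed the endline survey or met a main outcome". Only then is the release faxed to the records department "at every hospital where the participant reported visiting in the last year".

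Two further subsections add routes. If a participant dies before the records are accessed, "we will request the legal guardian or spouse to sign a new form giving us permission to access their medical records". If a participant withdraws, "we will ask them if it is still okay for us to access their medical records", and the standard procedure follows if they agree.

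The section on exiting the study lists more outcomes than these. Among them are "Unable to Continue (you should mark this answer if the person is too sick to continue", "Unable to Locate" and Unknown. The section on missing data points says of people who cannot be contacted within a window that "they have not exited the study but this is considered missing data". No chart-review route is given for any of these.

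**The concern.** A participant can sign the release at month 6, then become too ill to go on or drop out of contact, and under the stated rule the release stays in the cabinet. The people affected are plausibly heavier users of hospitals, or people whose reporting is less reliable, although the documents do not establish either. Emergency department use and hospitalization are two of the three components of the primary outcome in the SAP's sample size section, and the chart review is the check on how well they are reported. If that check omits these people, it cannot show whether self-report is accurate for them. If the omissions differ between the peer-support and control groups, it also cannot rule out a difference in reporting between groups.

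**Working it through.** **1. The plan's own figure.** The only power calculation is in the SAP's sample size section: 720 participants in total, two-sided 0.05. Assuming 1:1 allocation overall (360 per group) and effects in SD units, power = Φ(d·√(360/2) − 1.96). For d = 0.209, 0.223 and 0.242 this gives 0.801, 0.849 and 0.901, against the stated 0.80, 0.85 and 0.90. The figure reproduces, and no chart-review quantity enters it.

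**2. Each end-of-study status set against the request routes, for someone with a signed release.**

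| Status | Route to a records request |
|---|---|
| Endline completed, including late | Yes, standard trigger |
| Main outcome met (probably the Censored code, a move to higher care) | Yes, standard trigger |
| Unwilling to Continue | Yes, if the participant agrees when asked again |
| Withdrawn by study staff | Arguable under the withdrawal subsection |
| Deceased | Conditional on a new form from guardian or spouse, unless records were already obtained |
| Unable to Continue, no main outcome | None stated |
| Unable to Locate | None stated |
| Unknown | None stated |
| Not exited, endline never obtained | None stated |

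The last four rows are the gap. Main outcome is not defined in the supplied text; the table takes it to include a move to a higher level of care.

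**3. What could be recovered.** Hospitals are identified from the participant's own reports. For someone lost after month 6, only the period already reported (for instance at the 3- and 6-month contacts) can be checked. That part is recoverable, because the reports and the release are both on file.

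**4. What the gap can do to the result.** Let f be the share of signers with no route, A_c the proportion of signers with a route whose report agrees with the record, and A_u the same proportion among those without one. Agreement over both is (1 − f)·A_c + f·A_u, so the checked group differs from the whole by

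A_c − [(1 − f)·A_c + f·A_u] = f·(A_c − A_u).

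Both proportions lie between 0 and 1, so the difference is at most f in absolute value. It is zero if agreement does not depend on exit status. Neither document gives f, A_c or A_u. Taking f = 5%, 10% or 15% purely as assumptions, the limits are 5, 10 and 15 percentage points.

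**The case against.** The best defence is that the Protocol's enrollment section names three reasons to exit someone: withdrawal of consent, death and a main outcome. Each has a route, and the longer list is only a database menu. Someone too sick to continue might be treated as withdrawing, or might move to higher care and so meet a main outcome. Staff go on seeking a missed survey after its window, and a late endline does trigger the request. Nothing forbids a request in the remaining cases.

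Part of this stands. The lack of a route is an inference from silence, and late endlines and moves to higher care are taken as covered. But the exit list separates Unable to Continue from Unwilling to Continue, so reading illness as withdrawal is strained. Unable to Locate, Unknown and an endline never obtained fit no route on any reading.

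Three stronger readings are tempting and not supported.

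- A reader might infer that only completers are checked. The rule also covers main-outcome cases, withdrawers who agree, and deaths with a new form.
- A reader might infer that records are simply lost for everyone who leaves or dies in months 6 to 12. Withdrawers are asked again and a form is sought for deaths. Because requests wait for completion, most deaths on study do need that new form, but the documents do not say how often it can be had.
- A reader might compute how far the charted sample understates mean utilization, f(RR − 1)/[1 + f(RR − 1)], where RR is the event rate in the uncovered group relative to the others. With f = 0.10 assumed, this is 0.10/1.10 = 9.1% at RR = 2 and 0.20/1.20 = 16.7% at RR = 3. The arithmetic is right but the quantity is not one the plan estimates. The chart review tests agreement, and omitting heavy users does not by itself shift agreement.

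**Conclusion.** The point holds as a gap in the trigger for the chart review. Followed as written, the rule makes the validation sample selective: signers who exit as Unable to Continue without a main outcome, as Unable to Locate or as Unknown, and signers with no endline, are left out despite a release on file. The consequence is limited to what the validation can show. The SAP does not use chart data, so neither the primary estimate nor its power changes directly. The documents give no loss rate, so the number affected and the effect on agreement cannot be stated beyond the bound above. The conclusion rests on the natural reading of the exit list, on main outcome including a move to higher care, and on the release permitting a request before the endline. The form itself is not among the supplied documents.

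**What to change.** Change the trigger in the Medical Chart Review section to a signed release plus whichever comes first of: endline completed, main outcome met, any other study exit, or close of the 12-month window (8 weeks after the anniversary). Limit the request to the period for which visits were reported and to what the release permits. Keep the existing steps for withdrawals (ask again) and deaths (new form). Report chart-review coverage and agreement by study group and exit reason.

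The cost is a protocol sentence, a modest number of additional requests, and a check that each release is still valid. A participant who re-enters, or who gives an endline after the window has closed, may need a supplementary request.

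A separate request for months 0 to 6 at signing would secure those records before a later death or loss. It is optional. It adds a second round of faxes to every reported hospital, four-weekly follow-up and data entry, and it would not remove the need for a new form covering the months between that request and a death.

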Enrolling people in the study is a three step process. Step 1, is technically a pre-screen, we only want to upload people into DatStat who we think are eligible. If for whatever reason we find out that they are not eligible then we don't want them in the database. You can email [name] and she will delete their entry from DatStat. It is also a good idea for all RAs to keep a list of participants that have been deleted to ensure that you don't accidentally contact them again. Step 2 is the formal screening. If during the formal screening it turns out that they are not eligible then DatStat marks them as ineligible, and they will be removed from your workflow. They do not need to be formally exited from the study. Step 3 is when they sign the consent form during the baseline survey. Once they sign the consent form then, they are officially enrolled in the study. Moving forward, if for whatever reason the person withdraws consent, dies or meets a main study outcome that would be when you officially exit them from the study using the exit survey. The rule of thumb is we only exit people from the study who are officially enrolled, and people are only officially enrolled once they sign the consent form.

Updating or changing participant information once enrolled in study

When updating or changing participant information in Discovery, you can update participant information however you like, including assigning someone to the most accurate study group, prior to the participant signing the consent form. Once a participant signs a consent form, at that time we will consider all the information entered in Discovery to be updated and accurate. At this point some very critical variables such as study arm, race, age, gender, site, language, DOB, can never be changed, even if they are wrong. If at any time after the participant signs a

consent, you realize there is an error in one of these data categories you cannot change the information in Discovery but rather you need you to record that information in a participant log (a word document that you will keep on your computer) and you need to alert [name] of the change. Every few months [name] will ask for a copy of these participant logs. The participant log should include the Participant ID number, the person who made the change in the DatStat system, the original incorrect value and the new corrected value.

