If a participant has exited the study prematurely and contacts study staff about re-entry, the participant is only eligible to participate if

- a. They are still within the 1 year follow up period. In this case study staff will begin contacting participant at appropriate time points and other data will be considered missing.

- b. They sign a new consent form
- c. PI and Site PI agree to allow him/her to re-enter.

**Participants will never be allowed to collect more than \$100 for participation in the study

Payment

Completion of baseline= \$25

Completion of sixth month survey = \$25

Completion of endline survey at 12 months = \$50.

Regular Payment Schedule

Time Zero: \$25

12 Months: \$75

If a participant drops out after 6 months each organization will send the participant the \$25 they have earned.

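### Re-entry rule sets hospital, ED and placement events in the gap to missing, although the returning participant can be asked about them and the gap may be related to the outcome

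*Protocol*

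**What the plan says.** **Protocol, Reentry into the study after exited.** Return has three conditions: (a) "They are still within the 1 year follow up period"; (b) a new signed consent form; (c) "PI and Site PI agree to allow him/her to re-enter". No criterion is given for (c). On the data, the rule is: "In this case study staff will begin contacting participant at appropriate time points and other data will be considered missing". No step asks about events during the absence.

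**Protocol, Missing Data Points for a Participant.** Someone not reached within the window has not exited. The contact counts as missing, yet of such missed points the staff are told "they should still try to collect the data". They use an ad hoc survey, make a log entry, and note that the data were out of window and why.

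**Protocol, Exiting the Study.** The exit reasons include "Unable to Continue (you should mark this answer if the person is too sick to continue" and "Censored (moved to a higher level of care- i.e. independent care to assisted living". Staff enter a reason, a date and a comment for the participant, who is then no longer contacted. Under Enrollment in Study, exit follows when a person "withdraws consent, dies or meets a main study outcome".

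**Protocol, Medical Chart Review.** The aim is to compare self-report with the record. For people who withdraw, "we will ask them if it is still okay for us to access their medical records".

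**SAP.** The Analysis Plan expects random drop-out and refers missing data to an outside report. The Sample Size Justification names the annualized event rate as the primary outcome. Neither mentions re-entry or says which person-time forms the denominator.

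**The concern.** A re-entrant is available, willing and newly consented. The primary outcome consists largely of dated events that can be asked about afterwards, unlike a self-rated scale for a visit that has passed. The rule nevertheless declares the interval missing.

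The interval is not an arbitrary one. A person who exits as too sick and later recovers may well have had hospital or ED contact in between. Missingness would then be related to the outcome, which is not what the SAP expects. If the gap time still counts in the annualized denominator while its events do not, that group's rate is understated. If re-entry or hidden events differ between groups, the comparison shifts as well.

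**Working it through.** **1. The plan's own benchmark.** Inputs from the SAP: N = 720, two-sided 0.05. I assume two groups of 360; 1:1 allocation is stated for AJFCS, and the Protocol's site goals are split evenly. Detectable effect = (1.960 + z for power) × √(2/360), with √(2/360) = 0.0745:
- power 0.80: 2.802 × 0.0745 = 0.209
- power 0.85: 2.996 × 0.0745 = 0.223
- power 0.90: 3.242 × 0.0745 = 0.242

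The SAP's figures reproduce. I use 0.209 as the yardstick.

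**2. What is lost under the rule.** The exit form asks for reason, date and comment, not for events. The uncollected interval therefore starts at the last completed contact, which may precede the exit date. A move to a higher level of care that itself caused the exit is recorded with its date. Hospital and ED events in the interval, and any later placement, have no stated route in except chart review.

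**3. Whether another source covers it.**
- Chart review needs its own consent. Requests go only to hospitals the participant reported using, so a stay never asked about may never be requested. Its stated role is checking, not filling in outcomes.
- The next survey might reach back, but the survey documents are not provided. The nine-month script opens by saying three months have passed since the last conversation, which suggests a fixed recall period.

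**4. Possible size (assumptions only).** The documents give no exit, re-entry or event rate. Let r be the share of a group that re-enters, m the hidden events per re-entrant, and keep the full year in the denominator. A group's mean rate falls by r × m. The shift in the comparison is (r_A − r_B) × m / SD. With m = 1:

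| r_A | r_B | Shift, SD 1 | Share of 0.209 | Shift, SD 1.5 |
|---|---|---|---|---|
| 1% | 0 | 0.010 | 5% | 0.007 |
| 2% | 0 | 0.020 | 10% | 0.013 |
| 5% | 0 | 0.050 | 24% | 0.033 |
| 10% | 0 | 0.100 | 48% | 0.067 |
| 5% | 2.5% | 0.025 | 12% | 0.017 |
| equal | equal | 0 | 0 | 0 |

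A second set of assumptions gives the same order. Take 1–3% re-entry with 1–2 hidden events, and a negative binomial count with mean 0.6 and dispersion 2, so SD = √(0.6 + 2 × 0.36) = √1.32 = 1.15. The loss is 0.01 × 1 = 0.01 to 0.03 × 2 = 0.06 events per person, or 0.009 to 0.052 SD. That is 4% to 25% of 0.209, again only if all re-entry is in one group.

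**5. Why the denominator matters.** Take a re-entrant with one recorded event in nine observed months and one hidden event in a three-month gap (illustrative). Gap time kept: 1/1.00 = 1.00 per year. Gap time excluded: 1/0.75 = 1.33. Events collected: 2/1.00 = 2.00. Exclusion helps but does not recover an event-rich gap; collection does.

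**The case against.** The strongest reply is that the exit creates the gap, not the re-entry rule. Without re-entry all later follow-up would be missing too, so the rule recovers data. Illness exits without return are the larger problem, and this point does not touch them. That stands, but it does not explain why obtainable events are set aside once the person is back.

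Several stronger readings are tempting and should not be made:
- **That the hospital stay behind an exit is deleted.** A hospital stay is not a listed exit reason, and nothing says recorded events are removed. The Enrollment in Study wording about meeting a main study outcome is undefined and should be reconciled with the exit list; it does not show that a stay triggers exit.
- **That the two rules contradict each other.** Late collection is written for people who have not exited, and re-entry for people who have. The rules differ in thoroughness but cover different people.
- **That the bias favours one group.** Within a group, events can only be lost. Between groups, the sign depends on which group loses more, and the documents do not say.
- **That unblinded staff choose who returns.** The ID suffix shows the group and no blinding is described, but the participant makes the approach and re-consents, and the PI and Site PI decide. Nothing suggests approval varies by group.
- **That re-entrants hold a marked study calendar.** Reminder postcards go to active participants only; use of the calendar after exit is not shown.

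**Conclusion.** The point holds as a minor one. The re-entry rule sets gap data to missing although hospital, ED and placement events could be asked for, and the interval is plausibly related to the outcome because illness is an exit reason. The SAP's expectation of random drop-out does not cover this, and the SAP has no rule for gap person-time.

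The effect is probably small and cannot be computed from the documents. On assumed rates of 1% to 5% in one group only, with one hidden event each and SD 1, the shift is 0.01 to 0.05 SD, or 5% to 24% of the 0.209 detectable effect. It halves if the other group re-enters at half the rate and disappears if losses are equal, although both groups' rates are then still understated when gap time is counted. The conclusion also assumes that the surveys used after re-entry do not already ask back to the last completed contact, which cannot be checked here.

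**What to change.** **Protocol, re-entry section.** Replace the clause that declares other data missing with: *hospital, ED and placement events since the last completed contact are collected at re-entry using the out-of-window procedure and flagged; only self-rated scales for missed visits are missing.* The new consent form should say that these events will be asked about.

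**SAP.** State that gap time for which events could not be collected is excluded from the annualized-rate denominator. Add a sensitivity analysis without the flagged intervals, and report re-entries by group.

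**Condition (c).** Keep it. Automatic return on (a) and (b) alone would readmit people who exited because they moved to a higher level of care or were removed by staff. At most, have the PI and Site PI decide without reference to study group.

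**Cost.** Wording changes and a few minutes at the re-entry contact. The late-collection steps are written out for the three-month survey, so an equivalent is needed for the other time points. The real downside is longer recall for these intervals, which the flag allows to be examined.
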